Autonomic hyperreflexia occurs during the life of up to 85% of patients with a complete spinal cord injury above T₅. This occurs due to excessive sympathetic response to stimuli below the level of injury, absent the brain's normal damping effect [50]. As a result, exaggerated hypertensive responses can be expected due to surgical stimuli that can be properly blocked by deep anesthesia, or vasoactive agents. In a large case series (n=271 individuals with SCI at T₅ or higher), 16% of patients experienced mild or severe autonomic hyperreflexia in the presence of anesthesia [51]. However, all but ten of these

cases involved urological procedures. Since the current study involves a neurosurgical procedure, the stimuli will be above the level of the lesion and therefore the risk of hyperreflexia is reduced. Also, in response to hypertensive episodes, significant bradycardia can occur due to unopposed parasympathetic cardiac tone that can be treated with vasoactive agents.

Patients with chronic SCI also have a risk of deficient body temperature regulation due to loss of supraspinal regulation requiring meticulous management of hypothermia. An additional anesthesia-related risk in chronic SCI patients is an increased incidence of atelectasis postoperatively due to respiratory muscle compromise requiring extended controlled or assisted ventilation and chest physiotherapy, as well as postural drainage. Based on the literature and our experience, we believe the risks of anesthesia that are specific to SCI to be infrequent (1-10%).

After a neurosurgical procedure, common minor risks include mild to moderate headache, eyelid swelling, bruising around the eye, minor swelling of the incision, and minor CSF leaks that are easily stopped [52]. These risks are common to implantation and explantation of the device.

Steps taken to minimize these risks:

Participants will undergo pre-operative labs and screening at the Pre-Op Anesthesia Clinic to ensure that they are not deemed to have an increased surgical risk beyond the increased risk that is associated with spinal cord injury or other neurological disease/condition.

The director of Neuroanesthesiology at UPMC will oversee anesthesia care for participants in this study to ensure that participants are monitored adequately to allow for rapid intervention. As an additional layer of protection for responding to autonomic hyperreflexia, an A-line (intra-arterial catheter) will be inserted to allow for rapid intervention if necessary. In order to minimize autonomic hyperreflexia-related risk, participants with cardiovascular disease and coagulopathies (identified by pre-operative screening) will be excluded from this study.

We will follow the standard clinical procedures to minimize the risks associated with surgical implantation or removal of electrodes. For example, antibiotic prophylaxis administration is usually initiated for the patient approximately two hours before the surgery and will be maintained as directed by the study neurosurgeon and their clinical team. We have excluded pregnant females and those with renal failure as they may be at an increased risk for complications resulting from administration of the antibiotics. Complications or side effects usually result from prolonged dosing, rather than the single dosing that will be administered in this study. Antibiotic ointment and sterile dressings will be applied to the implantation site to minimize the risk of infection. Standard sterile surgical techniques will be followed for this study. This includes sterilization of the NeuroPort Arrays before the surgery and proper handling of NeuroPort Arrays during the surgery. The Patient Pedestals will be covered with antibiotic ointment and sterile dressings. These procedures will greatly

minimize the risk of infection. The NeuroPort Arrays will be placed away from blood vessels to minimize the risk of bleeding/bruising. Sufficient padding will be used to reduce the risk of pressure sores during surgery and individuals with a recent history of pressure sores will be excluded from participation.

Risks of Chronic Recording with NeuroPort Arrays (Core Study and Extension Study)

The primary risks of chronic recording center around the long-term presence of the NeuroPort Arrays and Patient Pedestals. The risks associated with the chronic implantation of the NeuroPort Arrays are expected to be similar to those observed with the implantation of other chronic devices such as deep brain stimulators and cochlear implants. Some of these include, but are not limited to thrombosis, embolism, body rejection phenomena, neurological complications, and infection (meningitis and cellulitis) (see full list below). The most common complication for these types of devices is infection. Infection rates for other implanted devices requiring a craniotomy range from 4 to 12% [20-22]. The outcome of infection may be serious and may lead to brain edema or other sequelae. If the infection cannot be treated with antibiotics, the NeuroPort Arrays may need to be explanted. Some of these procedures included in the infection risk estimate are more invasive than that proposed in the current study. Because we will perform a smaller craniotomy with a wound closure away from the implantation site, and due to the lack of clinical adverse events observed in the BrainGate trial, we believe that the risk of infection for a single NeuroPort Array is at the low end of this range (approximately 5-6%). Based on our team's experience with other neurosurgical procedures, we estimate the elevated risk of infection due to the presence of two percutaneous Patient Pedestals to be less than 50% of the current risk. Therefore the expected risk of infection for the proposed study is approximated to be less than 9%. Most of the risk for infection is due to environmental factors in the operating room and therefore having two percutaneous sites only introduces an incremental increase in the risk of infection.

There is also the potential for seizure and other neurological sequelae due to the presence of a chronic implant in the brain. It is possible that a subject that has limited ability to move finger(s) may lose that ability due to implant of the NeuroPort Array. It is unlikely that local tissue damage resulting from the inflammatory response will lead to functional deficits. No such deficits have been reported in any of the previous animal or human studies. As a point of reference multiple subpial transections, in which a series of shallow cuts are made into the cortex, are performed for treatment of intractable epilepsy where the seizure foci are located in areas of the brain that cannot be removed safely, such as the motor cortex. Major complications with this type of procedure are rare and neurological deficits appear to be only temporary [25, 26]. While unexpected, if any serious adverse events occur and they are resistant to treatment, the PI will recommend to the subject that the NeuroPort Array be explanted. Subjects will be followed for at least three weeks post-explant, and longer, if clinically necessary.

Based on published literature, and our plan for continued wound care and clinical monitoring, we do not believe that extending the implantation duration increases the risks of chronic implantation.

Table 2 summarizes possible risks, along with a brief definition, that may occur due to implantation and chronic recording with NeuroPort Arrays. Due to the limited number of human studies with the NeuroPort Arrays, it is difficult to provide quantitative estimates for each possible risk. However, based on published reports and discussions with BrainGate investigators, we expect the risk of serious or chronic adverse events to be very low. Based on our experience with other common neurosurgical procedures (such as deep brain stimulation and electrocorticography monitoring), we have provided our best estimate of the expected rate of occurrence for each clinical event.

Table 2. Possible risks of chronic implantation of the NeuroPort Array

Risk	Definition	Rate of Occurrence Rare: <1% Infrequent: 1-10% Common: >10%
Additional paralysis	Permanent or temporary loss or impairment of the subject's ability to move a body part	Rare
Adverse reaction to anesthesia	Reaction to any anesthetic agent given	Rare
Allergic reaction	Hypersensitivity reaction to a particular allergen	Infrequent
Ataxia of neck and facial muscles	Loss of the ability to coordinate muscular movement of the neck and facial muscles	Rare
Attention deficit	A deficiency or impairment in ability of the subject to concentrate	Rare
Autonomic dysreflexia	Paroxysmal rises in blood pressure	Rare
Bald spot	Lacking hair	Common
Blood clot	Blood clot (near surgical site)	Infrequent
Cognitive deficit	A permanent or temporary deficiency or impairment in mental functioning	Rare
Cramping	A sudden, involuntary, spasmodic muscular contraction causing severe pain, often occurring in the leg or shoulder as the result of strain or chill	Rare
Death	Subject death	Rare
Diplopia	A disorder of vision in which a single object appears double	Rare
Disequilibrium	Loss or lack of stability or equilibrium	Infrequent
Dizziness/vertigo	Having a whirling sensation and a tendency to fall	Infrequent
Dysarthria	A disturbance of speech due to emotional stress, to brain injury, or to paralysis, in coordination or spasticity of the muscles	Rare
Dysphagia	Difficulty in swallowing	Infrequent

Encephalitis	Inflammation of the brain	Rare
Epidural hematoma	A localized swelling filled with blood resulting from a break in a blood vessel located on or over the dura mater	Rare
Erosion around lead or pedestal	An eating or gnawing away of the tissue around the pedestal	Infrequent
Erythema along lead tunnel or pedestal	Redness of the skin caused by dilatation and congestion of the capillaries	Common
Exacerbation of underlying motor deficit	Temporary aggravation of the preexisting basic or fundamental motor deficit	Infrequent
Facial paresis	Paralysis of the face	Rare
Fatigue	Temporary physical or mental weariness resulting from exertion	Common
Fever	Abnormally high body temperature	Infrequent
Hemorrhage	Excessive discharge of blood from the blood vessels; profuse bleeding	Rare
Headache	A pain in the head	Common
Histotoxic reaction	The chronically implanted components have a poisonous effect on the tissues	Rare
Hoarseness	Having or characterized by a husky, grating voice	Infrequent
Hypersensitivity to Chlorhexidine	Highly or excessively sensitive to chlorhexidine	Infrequent
Immune rejection	The failure of the body to accept implanted material as a result of immunological incompatibility; immunological resistance to foreign material	Rare
Incision site pain	Temporary pain along the cut made during surgery	Common
Infection	Invasion by and multiplication of pathogenic microorganisms in a bodily part or tissue, which may produce subsequent tissue injury and progress to overt disease through a variety of cellular or toxic mechanisms. One type of infection is cellulitis or insertion site skin infection	Infrequent
Inflammatory process	A protective tissue response to injury or destruction of tissues	Infrequent
Intraparenchymal hemorrhage	Excessive discharge of blood from the blood vessels; profuse bleeding occurring within the parenchyma	Rare
Lead migration	A spontaneous change in the place of the lead	Rare
Loss of residual movements	Loss of any movements that the subject had prior to the surgery	Rare
Meningitis	Inflammation of the meninges of the brain and the spinal cord, most often caused by a bacterial or viral infection and characterized by	Rare

	fever, vomiting, intense headache, and stiff neck	
Nausea	Nausea	Common
Neck dystonia	Abnormal tonicity of muscle, characterized by prolonged, repetitive muscle contractions that may cause twisting or jerking movements of the neck	Rare
Neck pain	An unpleasant sensation occurring in varying degrees of severity as a consequence of injury or disease in the neck	Rare
Neck paresis	Paralysis of the neck	Rare
Neurological deficits	A permanent or temporary deficiency or impairment in neurological functioning	Infrequent
Non healing wound	A wound that because of infection or disease will not close with granulation tissue	Rare
Numbness	Deprived of the power to feel normally	Rare
Pedestal site drainage	Fluid leaving the pedestal site	Rare
Pedestal site ecchymosis	The passage of blood from ruptured blood vessels into subcutaneous tissue, marked by a purple discoloredation of the skin	Common
Pedestal site pain	An unpleasant sensation occurring in varying degrees of severity as a consequence of injury or disease	Infrequent
Percutaneous site infection	Invasion by and multiplication of pathogenic microorganisms in the area of the pedestal	Infrequent
Perioperative bleeding	Bleeding during surgery	Rare
Post-operative bleeding	Bleeding after surgery	Rare
Psychiatric episode	Mental and emotional disorder of brief duration	Infrequent
Scalp necrosis	Scalp tissue that dies	Rare
Scalp numbness	Deprived of the power to feel the scalp	Common
Scarring	Scar at site of implant/explant	Common
Seizure	A sudden attack, spasm, or convulsion, as in epilepsy or another disorder	Infrequent
Sensor migration	Sensor moves outside the primary motor cortex	Rare
Skin inflammation	A localized protective reaction of skin to irritation, injury, or infection, characterized by pain, redness and swelling	Common
Skin irritation	A condition of inflammation, soreness, or irritability of the skin	Common
Spasticity	A state of increased tone of a muscle	Rare
Speech deficits	A deficiency or impairment in mental or physical function of speech	Rare
Stroke	Sudden loss of brain function caused by a blockage or rupture of a blood vessel to the	Rare

	brain, characterized by loss of muscular control, diminution or loss of sensation or consciousness, dizziness, slurred speech, or other symptoms that vary with the extent and severity of the damage to the brain	
Subarachnoid hemorrhage	Excessive discharge of blood from the blood vessels; profuse bleeding occurring beneath the arachnoid membrane	Rare
Subdural hematoma	A localized swelling filled with blood resulting from a break in a blood vessel located or occurring beneath the dura mater	Rare
Tissue granulation	Small, fleshy, beadlike protuberances, consisting of outgrowths of new capillaries, on the surface of a wound that is healing	Common
Wound healing difficulties	Occurs when wound does not heal as expected or within expected time frame	Infrequent
Vocal cord paresis	Paralysis of the vocal cord	Rare

Steps taken to minimize these risks:

Several steps have been taken to mitigate potential risks associated with the NeuroPort Arrays. By design, the NeuroPort Arrays have a small profile to minimize impact to the cortex tissue and thereby reduce bleeding following insertion. This means that a relatively small craniotomy can be made in comparison to other procedures such as invasive epilepsy monitoring.

To minimize tissue damage at the site of implantation, a pneumatic Array Inserter tool which standardizes the implantation of the NeuroPort Array, will be provided. The tool inserts the Sensor at a specific rate and is designed to cause minimal tissue damage. Animal studies of the NeuroPort Array have shown little or no tissue damage at the implantation site. Due to the subject's preexisting condition this area of the brain has been essentially disconnected from communicating with other parts of the body. So, the visible effects directly related to potential injury to the primary motor cortex tissue are expected to be insignificant and are not anticipated to compromise the subject's medical or neurological baseline status.

The device materials in contact with the body are known biocompatible materials. Animal study results of the NeuroPort Array reveal an absence of, or a limited observed, systemic toxic effects or adverse neurological effects.

Because the pedestal protrudes through the skin, there is a risk of infection even after surgical healing and recovery. The risks of the long-term presence of the Patient Pedestal are minimized by an infectious disease screen, frequent checks performed by a caregiver, and a specific wound/skin care procedure designed to reduce the chance of infection. The protocol describes steps taken before and during surgery to create a sterile environment and to exclude individuals who may be at high risk for infection. Participants will also undergo immediate post-operative care in the neurosurgical

ICU, neurosurgical medical surgery recovery unit, and the UPMC Rehabilitation Institute. During ongoing device use, a family member or caregiver will be instructed to inspect the Patient Pedestal site daily. The Patient Pedestal will be cleaned at least every 7 days. Also, we will monitor the subject's temperature each day when BMI training occurs since this is a reliable indicator of infection. The subject will also be instructed to monitor and record their temperature daily. This will allow us to provide appropriate clinical care in a timely manner.

Risk of Fibrosis due to Chronic Implantation (Core Study and Extension Study)

There is a risk that it may not be possible to remove one or both of the arrays due to fibrosis (excessive tissue growth). We believe that it is very unlikely (<1%) that this will occur. If the risk of damage to the cortex outweighs the priority to remove the Arrays, our surgeon sub-investigator would cut the lead wire and remove the pedestal(s) leaving the 4 x 4 mm array(s) implanted. The risk of migration would be minimal since the array would be encased in the fibrous tissue. It is possible that the participant may not be able to have an MRI if the array(s) remains implanted since MR safety guidelines differ between institutions. The procedure for evaluation would be similar to other devices that remain implanted near the brain such as titanium plates, metal (aneurysm) clips, and silastic catheters. We do not expect that additional follow-up, beyond the 2 planned visits (1 and 4 weeks post explant) with the neurosurgical team, will be required. We do not believe that extending the implantation duration for up to 5 years increases the risk of fibrosis that would make it more difficult to remove the array.

Steps taken to minimize these risks:

The neurosurgeon sub-investigator will evaluate the extent of fibrosis prior to removing the arrays and determine whether they can be removed safely. The neurosurgeon sub-investigator is board-certified and experienced in removal of implanted devices. Based on our experience with non-human primate research at the University of Pittsburgh and the published results of the human BrainGate trials, we believe that the risk of having to leave the arrays implanted is very low (<1%).

Risks of Post-Operative Head CT (Computed Tomography) (Core Study)

The amount of radiation exposure that participants will receive from the head CT is approximately 2-5 rems (a unit of radiation exposure) to the area of the body evaluated with minimal exposure of other areas of your body. For comparison, this is a small fraction (<25%) of the annual radiation exposure (20 rems) permitted to the most sensitive organs of radiation workers by federal regulations. There is no minimal level of radiation exposure that is recognized as being totally free of the risk of causing genetic mutations (abnormal cells) or cancer. However, the risk associated with the amount of radiation exposure that the subject will receive from this study is considered to be low. A head CT will only be conducted as part of the extension study if ordered by the neurosurgeon to investigate a change in the participant's neurological status.

Steps taken to minimize these risks:

It is standard clinical procedure to perform a head CT after a neurosurgical procedure in which electrodes are implanted. This allows for documentation of electrode location and can identify possible adverse reactions (such as bleeding or swelling) following surgery. The risk associated with the amount of radiation exposure that the subject will receive from this exam is considered to be low and comparable to everyday risks.

Risks of Post-Operative Head X-ray (Core Study)

The maximum amount of radiation exposure that participants will receive from the x-ray exam is approximately 0.3 rem (a unit of radiation exposure) to the area of the body evaluated with minimal exposure of other areas of your body. For comparison, this is a small fraction (1-2%) of the annual radiation exposure (20 rems) permitted to the most sensitive organs of radiation workers by federal regulations. There is no minimal level of radiation exposure that is recognized as being totally free of the risk of causing genetic mutations (abnormal cells) or cancer. However, the risk associated with the amount of radiation exposure that the subject will receive from this additional x-ray exam is considered to be low and comparable to everyday risks. A head x-ray will only be conducted as part of the extension study if ordered by the neurosurgeon to investigate a change in the participant's neurological status.

Steps taken to minimize these risks:

It is standard clinical procedure to perform a head x-ray after a neurosurgical procedure in which electrodes are implanted. This allows for documentation of electrode location. The risk associated with the amount of radiation exposure that the subject will receive from this exam is considered to be low and comparable to everyday risks.

Risks of BMI Training/Testing (Core Study and Extension Study)

During training, subjects will be asked to perform simple tasks that carry no risk above what is experienced during a typical daily routine. Subjects will perform simple movements or learn to control computer cursors or virtual objects. The research personnel will ensure that the behavioral tasks and their difficulty levels are set properly for each subject. We may ask them to attempt to control a prosthetic limb or robotic arm. Risks from interaction with the prosthetic or robotic arm or from dropping objects being transported by the arm include potential bruises or abrasions or minor damage to the participant's wheelchair. The risk of these is infrequent (1-10%) and precautions will be taken to minimize this risk. We may ask them to attempt to control a robotic arm exoskeleton (Figure 5). Risks from interaction with the exoskeleton arm would include possible injury to subject's arm if it moves past a comfortable joint position or if it collides with wheelchair or other parts of subject's body.

We may attach additional skin electrodes to record EMG or provide a ground for our BMI system. These electrodes are commonly used for this type of recording, but they may cause minor skin irritation. Also, we may stimulate peripheral nerves as part of our somatosensory testing which may cause discomfort or spasticity in some subjects. This testing can be stopped at any time.

In addition to physical risk, there is a psychological risk to participation in BMI training sessions. Individuals may experience frustration during the training, particularly early in the study. During the extension study, participants may experience frustration as signal quality starts to decline. Participants may have feelings of negativity or other emotional concerns during the study.

Steps taken to minimize these risks:

During training, subjects will be asked to perform simple tasks that carry no risk above what is experienced during a typical daily routine. The research personnel will ensure that the behavioral tasks and their difficulty levels are set properly for each subject. Testing can be stopped at any time and we will work with the subject to determine session start time and duration. Investigators will be present during all testing sessions to ensure safe operation of any external devices that are used. Safe operation will be ensured in a variety of ways including manual override control by the operator, slow operation speed of the device, and defined workspaces that prohibit contact between the participant and the technology.

In order to avoid risks from close proximity with the prosthetic or robotic arm or robotic arm exoskeleton, the following precautions are in place: (1) ensuring the subject has demonstrated adequate brain control of the robotic arm when positioned at a safe distance away from the participant (judged by the sponsor/investigator, likely >75% success on simple reaching tasks), (2) ability to program the robotic arm or exoskeleton with appropriate workspace and/or range-of-motion limits and definitions, and (3) constant monitoring of interaction with the robotic arm or exoskeleton by the study team who have the ability to stop the robotic arm via computer control or manual power shut-off.

Figure 5: Robotic Arms: Modular Prosthetic Limb (LEFT) and ArmeoPower exoskeleton (RIGHT)

Since BMI testing requires frequent sessions and significant effort on the part of the participant, older participants may become easily fatigued and therefore we have limited our age group to 18-70 years. Additionally, frequent training is necessary to induce neuroplasticity and we believe it may be more difficult to induce neuroplasticity in older individuals.

Individuals may experience frustration during BMI training sessions, particularly early in the study. For the extension study, participants will be informed that it is likely that signal quality will degrade over time. This may make it more difficult to complete the tasks so the difficulty and complexity may need to be reduced. Participants can be scheduled for appointments to speak with a psychologist throughout the study (approximately 1, 3, 6 and 9 months after implantation and again prior to explantation) to discuss any concerns they have during the study. The visits will occur every 3 months during the extension study as well. In addition, physician-investigators may refer the subjects to additional psychological appointments at their discretion.

Risks of EEG/EKG Recording (Extension Study)

Minor skin irritation may develop from the placement and removal of EKG and EEG electrodes.

Steps taken to minimize these risks:

Cleaning the skin after removal of the electrodes will reduce the risk of skin irritation. If skin irritation does occur, an over-the-counter ointment can remedy this.

Risks of In-Home Sleep Evaluation (Extension Study)

Participant may experience fatigue following sleep evaluation, if amount of sleep was insufficient or below normal amount.

Steps taken to minimize these risks:

Participant and caregiver will be asked to ensure that participant does not perform any activities that would invite risk of injury until the fatigue has subsided..

Risks of Pregnancy (Core Study and Extension Study)

Women who are, or plan to become, pregnant are excluded from the study due to potential risks to the unborn fetus or themselves. These risks include radiation exposure during x-ray or CT imaging which may lead to birth defects, mental impairment, cancer, or miscarriage. There are no known risks associated with undergoing an MRI scan while pregnant and the risks of MRI to the fetus are felt to be very small, but are nevertheless also not known. Any complications during surgery would put the fetus at risk for distress. We do not believe that pregnancy would carry any additional risks while the array is implanted, however this has not been studied and therefore the risks are unknown.

Steps taken to minimize these risks:

Study investigators will discuss the risks of pregnancy during the course of the study and will advise women against becoming pregnant. Women will be advised to notify the study team immediately if they learn they are pregnant.

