2.5 Study outcome evaluations

2.5.1 Study endpoints

The NeuroPort Arrays will be removed 1 year (+/- 30 days) after implantation. A participant will be considered a success for safety if the device is not explanted for safety reasons during the 12-month post-implant evaluation. If the subject experiences treatment resistant (serious) adverse events, he or she will be withdrawn and the arrays will be explanted early (See Section E 2.4.4). The study may also end early if the subject is non-compliant (See Section E 2.4.4).

We believe it is possible that a participant will not want the array removed. If the participant wants the NeuroPort Arrays to stay in, the study PI and neurosurgeon will assess whether this is acceptable. This decision will be based on whether or not the participant is at increased risk by leaving the arrays in and whether the device is still measuring neural activity that is sufficient for brain control. We will consult our DSMB if conflicts arise. One participant in the BrainGate trial has had a NeuroPort Array implanted for more than 1000 days without adverse event [9]. If the NeuroPort Arrays remain implanted for more than 1 year, we will continue to perform clinical follow-up as described in the current protocol. We may also continue brain-machine interface testing although the frequency of the training sessions may be reduced. We will remove the NeuroPort Arrays at anytime as directed by the participant, or as dictated by their clinical condition.

If the participant wishes to leave the NeuroPort Array implanted, but the study PI and neurosurgeon do not feel that it is in their best interest, the participant will be counseled that they should have the NeuroPort Array removed and that not doing so could result in clinically significant adverse events. They will also be informed that brain-machine interface training will not continue. The consent form includes a statement that participants will be financially liable for any medical care resulting from complications of not having the device removed upon instruction of the study PI. We will however allow participants to have the device removed at anytime and the explantation costs would be covered by this study.

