3.5.2 Sample size determination

This is the first study to evaluate a long-term implantation of microelectrode arrays in individuals with spinal cord injury (or other impairment resulting in upper limb paralysis). Because this is a feasibility study, we feel that it is appropriate to begin with a small sample size in this initial investigation. We are recruiting up to 5 participants for PRO10080021 and only these people would be eligible for the current study.

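### The statement that longer implantation adds no chronic-implant risk conflicts with the protocol's own account of continuing pedestal infection risk, and the infection figure and Table 2 rates have no time base

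*Combined protocol and SAP*

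**What the plan says.** Section 4.1 (Risks of Chronic Recording with NeuroPort Arrays) is marked as applying to both the core and the extension study. Citing the literature in general terms, together with the planned site care and follow-up, it states a belief: "we do not believe that extending the implantation duration increases the risks of chronic implantation". The fibrosis subsection repeats the belief: "We do not believe that extending the implantation duration for up to 5 years increases the risk of fibrosis".

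The chronic recording subsection also:
- places the primary risks in the long-term presence of the arrays and pedestals;
- puts single-array infection risk at about 5–6%, adds less than half again for two pedestals, and arrives at below 9%;
- attributes most infection risk to the operating room;
- states, among the mitigation steps: "Because the pedestal protrudes through the skin, there is a risk of infection even after surgical healing and recovery".

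Table 2 bands each risk as Rare (<1%), Infrequent (1–10%) or Common (>10%). Infection and percutaneous site infection are both Infrequent. Neither the 9% nor the bands carry a period.

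On long exposure, section 3.5.2 says "This is the first study to evaluate a long-term implantation of microelectrode arrays in individuals with spinal cord injury", and section 2.5.1 cites one case: "One participant in the BrainGate trial has had a NeuroPort Array implanted for more than 1000 days without adverse event". Section 3.5.3 (Aim 1a) plans to document adverse events. It has no implant-time denominator, no separation of the first year from later years, and no interval.

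**The concern.** Two statements in section 4.1 cannot both hold for time-dependent events. If pedestal infection can occur at any time while the pedestal is in place, a participant implanted for up to 5 years has more cumulative risk than one implanted for 1 year. Without a period attached, a reader cannot tell whether the 9% and the Table 2 bands describe the first year, the whole implantation or mainly the surgery.

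Two things are at stake. Section 4.1 is the protocol's risk statement for the extension, and section 4.2.1 judges whether an event is unexpected or unanticipated partly by its stated frequency. That benchmark is undefined for later years if the rates have no period. Also, Aim 1a as planned would give no measure of how little an event-free run in at most 5 people can establish about added duration.

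**Working it through.** **1. The plan's own figure.** Single-array risk × 1.5: 5% × 1.5 = 7.5% and 6% × 1.5 = 9.0%. With an increment below 50%, this gives less than 9%, so the figure reproduces. The calculation contains no duration term.

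**2. What duration could do to it.** Inputs from section 4.1: total infection risk T = 7.5% or 9%; most of it from the operating room; some risk continuing after healing. Assumptions made here, not in the documents: T is a 1-year risk; a share s of it is a one-off perioperative risk, with most read as 50–100%; the rest is a constant yearly risk h.

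- h = 1 − (1 − T)/(1 − sT)
- 5-year risk = 1 − (1 − sT)(1 − h)^5
- risk in years 2–5 if infection-free at year 1 = 1 − (1 − h)^4

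Example, T = 9%, s = 50%: h = 1 − 0.91/0.955 = 4.71%; 5-year risk = 1 − 0.955 × 0.9529^5 = 25.0%.

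| s | h (T = 9%) | 5-year risk, T = 9% | 5-year risk, T = 7.5% | Years 2–5 if infection-free at year 1, T = 9% |
|---|---|---|---|---|
| 100% | 0 | 9.0% | 7.5% | 0% |
| 90% | 0.98% | 12.5% | 10.4% | 3.9% |
| 75% | 2.41% | 17.5% | 14.6% | 9.3% |
| 50% | 4.71% | 25.0% | 21.1% | 17.6% |

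At T = 9%, the 5-year risk passes 10%, the top of the Infrequent band, once s is about 97% or lower. If the 9% already covers the whole implantation, none of this applies and the figure stands.

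**3. What the cited long exposure supports.** One participant at 1000 days is 1000/365.25 = 2.74 years. With no event, the one-sided 95% Poisson upper bound from that case alone is −ln(0.05)/2.74 = 1.09 events per year.

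**4. What this study could show.** Up to 5 participants for up to 4 extra years gives at most 20 implant-years. Zero events would leave an upper bound of −ln(0.05)/20 = 0.15 per year. Year 1 contributes about 5 implant-years, with a zero-event bound of −ln(0.05)/5 = 0.60 per year. The chance of no event in 20 implant-years is exp(−20h). For assumed yearly hazards of 1%, 2%, 5% and 10% it is 82%, 67%, 37% and 14%.

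**5. Fibrosis.** The subsection gives below 1%, resting on primate work and published human trial results. No passage says the risk of a non-removable array grows with time, and none gives a figure by duration.

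**The case against.** The strongest reply is that the sentence is a stated belief resting on literature and continued monitoring, not a claim of equivalence, and that the literature cannot be checked from these documents. That stands. A reader might infer that the plan treats missing evidence as proof of no difference. The text does not go that far.

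A reader might also infer that the extension's risk figures are shown to be too low. They are not. The rates have no period, most infection risk is placed in the operating room, and section 3.3.3 admits only participants at least 6 months post-implant with no open significant adverse event. Their remaining risk could be below 9%; the last column of the table exceeds 9% only when s is about 75% or less.

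The sentence could also mean that the yearly risk does not rise with time. That is compatible with the rest of section 4.1, but cumulative risk would still grow, and the text does not say which is meant.

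Nor do the documents support two stronger consequences. Consent materials are held elsewhere in the IDE application, so what participants are told cannot be judged here. Too low a stated incidence would make an event more likely, not less, to count as unanticipated. Late events are also closely watched: there are monthly examinations, daily site checks and DSMB oversight, and section 4.2.5 sends wound problems to the DSMB Chairperson within 24 hours.

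None of this removes the conflict over pedestal infection, or supplies the missing period.

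**Conclusion.** The concern holds for time-dependent risks, chiefly percutaneous pedestal infection. There, the no-increase sentence is inconsistent with the rest of section 4.1, because any continuing risk makes cumulative risk over up to 5 years exceed that over 1 year. This direction needs no assumption beyond the protocol's own statement that risk persists after healing.

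The size is unknown. The range of about 9–25% at 5 years depends on reading 9% as a 1-year risk, on a perioperative share of 50–100% and on a constant late hazard. Under the whole-implantation reading the figure is unchanged. Perioperative items in Table 2 are unaffected. The fibrosis statement lacks duration-specific support in the documents but is not contradicted. Neither the single long exposure cited nor an event-free extension could establish that duration adds no risk.

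**What to change.** In section 4.1:
- Qualify the no-increase sentence to say that the cumulative risk of pedestal infection and other time-dependent events rises with time implanted, by an amount not yet known.
- State the period that the below-9% figure and the Table 2 rates cover, and separate perioperative from continuing risk.
- Say that the fibrosis belief rests on limited experience.

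In section 3.5.3 (Aim 1a), report pedestal infection and other device-related serious events per implant-year, for year 1 and for later years, with exact Poisson 95% bounds. Label this as description only. Note that extension entrants are selected under section 3.3.3, so the two periods are not a fair comparison, and that zero events in at most 20 implant-years still allows about 0.15 events per year.

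The cost is some rewording and one descriptive table from adverse events and implant dates already recorded, with no new procedures or participants. The downside is that the stated extension risk reads slightly less favourably.
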